### 20.2 Institutional Review Board

The institutional review board will review the conduction and continuation of the study from ethical, scientific, and medical/pharmacological perspectives based on the information contained in the investigator’s brochure, study protocol, and informed consent form/explanation sheet.

### 20.3 Preservation of Subject Confidentiality

All parties involved in the study will identify the subjects in the subject records and case report forms using the subject ID codes and will protect the confidentiality of the subjects when source documents pertaining to the conduct of the study are being accessed, published in medical journals, submitted to the regulatory authorities, etc.

## 21. Record Storage

### (1) Records stored at the study site

A storage manager appointed by the head of the study site will store the documents or records pertaining to the study that should be stored at the study site until 1) or 2) below, whichever comes later. However, if the study sponsor states that these documents or records should be stored for a longer period, the study site will hold discussions with the study sponsor about the term and method of storage.

If the study sponsor decided not to append the clinical study test result data that have been collected in the course of the study to the approval application form, the study sponsor will inform the study site directors of this fact, and of the reason(s) therefor, in writing.

In addition, if marketing approval is obtained for this investigational product, or if the study sponsor decides to discontinue development of this investigational product before approval is obtained, then the study sponsor will inform the study site directors of this fact in writing.

- 1) Date of marketing approval for the investigational product (if a notification has been received that development is being discontinued or the study results are not being appended to the approval application, then the date on which 3 years have passed since the date this information was received).
- 2) 3 years after the discontinuation or completion of the study

### (2) Records stored at the study sponsor

The study sponsor will store the documents or records pertaining to the study that should be stored at the study sponsor until 1) or 2) below, whichever comes later. However, because this investigational product meets the definition of a product of biological origin, records of its manufacture and use will be kept for at least 10 years from the date of approval.

- 1) The date marking 5 years since the date of marketing approval for the investigational product (if development is discontinued, the date marking 3 years from the date on which the decision was made to discontinue development) or the date marking the end of reexamination.
- 2) 3 years after the discontinuation or completion of the study

## 22. Monetary Payments

Payments of monetary compensation to subjects and study sites will be made in accordance with the contracts or memoranda of agreement between the study sites and the study sponsor.

## 23. Compensation for Health Injuries, and Insurance

### 23.1 Compensation for Health Injuries

If a subject suffers a health injury as a result of the conduction of this study, the study sponsor will compensate the subject appropriately, based on predetermined criteria, except in cases where a causal relationship to the study has been ruled out (said compensation will include the subject's medical treatment fee copayments, a medical allowance, and compensation money). In such cases, the subject will be under no burden to prove that there is a causal relationship.

### 23.2 Insurance

The study sponsor will take out insurance and will take any other necessary actions to ensure that the study sponsor is indemnified against health injuries experienced by subjects in connection with the study.

## 24. Agreement on Publication

The information that is contained in this study protocol is the property of the study sponsor, and although it will be provided to the institutional review boards and relevant parties, such as the (sub)investigators conducting the study, it must not be divulged to any outside party without the written consent of the study sponsor, unless this is necessary for the implementation of the study.

In addition, if the information that is obtained by the conduction of this study is going to be presented to any outside parties, such as at a specialist conference, by any study site staff involved in the study, such as a (sub)investigator, the consent of the study sponsor must be obtained in advance. Furthermore, the study sponsor may freely report the information obtained in this study to the regulatory authorities or for a purpose such as the appropriate use or marketing of the drug product.

8. SOFTWARE USED	14
9. CHANGES TO STATISTICAL ANALYSIS PLAN FROM THE PROTOCOL	14
10. REFERENCES	14

List of Abbreviation

Abbreviation	Unabbreviated term
PRP	Polyribosyribitol phosphate
Hib	Haemophilus Influenzae type b
PT	Pertussis Toxin
FHA	Filamentous Hemagglutinin
FAS	Full analysis set
MedDRA/J (The following terms are adverse event-related terms.)	Medical dictionary for regulatory activities/Japanese version
PT	Preferred Term
SOC	System Organ Class

Definition of Terms

Term	Definition
Day of vaccination	Day 1
Visit X or VX	Test/observation time point at the Xth visit

1. INTRODUCTION

This document describes the sponsor's plans for the statistical analyses of efficacy and safety in the "P3 study of BK1310 in healthy infants," and covers the information that is included in the study protocol, but in greater detail. Additionally, this document describes the analyses that will be performed for Cohort 1, and does not describe the plans for the statistical analyses being performed for Cohorts 2 and 3.

2. STUDY OBJECTIVE AND STUDY DESIGN

2.1. Objectives

[figure not shown]
To investigate on an exploratory basis the safety of BK1310 and its immunogenicity against Hib in healthy infants, and to then investigate on an exploratory basis the efficacy and safety of BK1310 using simultaneous vaccination with ActHIB and Tetrabik as the control.

2.2. Study Design

The study population will consist of the 3 cohorts described below (Cohort 1, Cohort 2, and Cohort 3). This statistical analysis plan describes the sponsor's plans for the statistical analyses that will be performed for Cohort 2.

(1) Cohort 1

A randomized, double-blind, parallel-group, multicenter study

Subjects randomized to the following groups will receive the following investigational products.

- BK1310 H group: Formulation H, 0.5 mL per dose

[figure not shown]
- BK1310 L group: Formulation L, 0.5 mL per dose

Subjects will receive 3 doses of investigational product, 0.5 mL for each dose, for the primary immunization, administered subcutaneously (upper arm extensor) at intervals of 3 to 8 weeks (standard vaccination interval: 4 weeks). For the booster immunization, subjects will receive a single subcutaneous (upper arm extensor) dose at 6 to 13 months after the primary immunization. However, the repeated vaccination of investigational product at the same location as that which was used for the previous dose will be avoided.

Once the assessments have been performed following the first vaccination with the investigational product to the last subject in Cohort 1 (after the primary immunization), and after the measurement of the antibody titer against Hib antigen (the anti-PRP antibody concentration) has been completed (at the time point shown in the figure above (*)), the blind will be broken, and the BK1310 safety information will be assessed, and once it has been confirmed that the subject has been afforded adequate immunity against Hib antigen, a decision about whether or not to initiate Cohort 2 will be made based on the criteria described in “5.2.2 Cohort 2 Initiation Criteria.” Additionally, except for the study sponsor, for whom the study will not be blinded after unblinding (except for the monitors, as described in “25.1.6 Monitors”), the study will continue with the double blind maintained even after unblinding.

(2) Cohort 2

A randomized, observer -blinded, active-controlled, parallel-group, multicenter study

Subjects randomized to the following groups will receive the following investigational products.

[figure not shown]
Furthermore, for BK1310 H and L groups, to which group each subject will be assigned will be decided after the completion of Cohort 1 and before the start of Cohort 2.

- BK1310 H and L groups: Subjects will receive 0.5 mL per dose of formulation H or L
- Control group: Subjects will receive 0.5 mL of each of ActHIB and Tetrabik

For the primary immunization,* subjects will receive 3 subcutaneous doses (as a rule, administered at the top part of the upper arm extensor) at intervals of 3 to 8 weeks (standard vaccination interval: 4 weeks). Subjects in the control group will receive subcutaneous doses of Tetrabik and ActHIB (as a rule, administered at the top and bottom, respectively, of the upper arm extensor on the same side). However, the repeated vaccination with investigational product at the same location as that which was used for the previous dose will be avoided.

*: The completion of the primary immunization series with the investigational product. For the booster immunization, a dose will be administered as part of, for example, routine immunization.

(3) Cohort 3

Only for subjects from whom written informed consent has been obtained, after the end of Cohort 2, and generally after 4 weeks have passed since the administration of the booster immunization received as part of, for example, routine immunization, the investigator will perform antibody titer measurements as a follow-up investigation, depending on the results that have been obtained after the primary immunization in Cohort 2, or in accordance with the wishes of the subject (subject's legal guardian).

2.3. Randomization Method

In this study, subjects will be randomly assigned to either the BK1310:H group or the BK1310:L group using a variable block method.

2.4. Assessment Time Point

The Cohort 1 assessment time points are shown below.

Day of consent	Visit 1			Visit 2			Visit 3			Visit 4		Visit 5		Visit 6	
	1st vaccination			2nd vaccination			3rd vaccination			Post-vaccination Examination 1		4th vaccination		Post-vaccination Examination 2	
	Before	Vaccination	After	Before	Vaccination	After	Before	Vaccination	After	Before	After	Vaccination	Before	After	
Allowable window	D1			Visit 1 + 3 - 8 weeks			Visit 2 + 3 - 8 weeks			Visit 3 + 4 - 6 weeks		Visit 3 + 6 - 13 months		Visit 5 + 4 - 6 weeks	
Written informed consent	•														
Investigation of subject background		•										•			
Examination	•		• ^{*1}	•		• ^{*1}	•		• ^{*1}	•	•	•	• ^{*1}	•	•
Body temperature measurement (axillary)	•			•			•				•				
Investigational product vaccination			•			•			•			•			
Blood sampling (antibody titer)	•										•	•		•	• ^{*2}
Adverse events ^{*3}				•			•			•			•		
e-Diary ^{*4}															

*1: Subjects will be asked to wait in the hospital for 30 minutes after receiving the investigational product, and will be examined 30 minutes after vaccination.

*2: Blood samples will be collected for antibody titer measurement only at discontinuation after the third or fourth dose of the investigational product has been administered.

*3: An investigation will be performed to confirm whether or not the subject experienced any adverse events during the period from Visit 1 to Visit 4, and during the period from Visit 5 to Visit 6, based on examination of the subject at the study visits and based on the subject's e-Diary. Only serious adverse events will be investigated during the period from Visit 4 to Visit 5.

4: Every day until 14 days after each dose, if the subject's symptoms have not returned to normal by Day 14, then the subject will be asked to, as a rule, fill out the e-Diary until the symptoms return to normal.

2.5. Sample Size Justification

○ Target sample size

Cohort 1: 30 subjects (BK1310 L group: 15 subjects; BK1310 H group: 15 subjects)

Rationale

In Cohort 1, the sample size was set at 15 subjects per group, 30 subjects in total, as the number of subjects that will make it possible to confirm that the anti-PRP antibody concentrations and antibody

seroprotection rate have not decreased appreciably, in order to confirm that combining the vaccines does not result in a reduction in Hib antigen immunogenicity.

3. ENDPOINTS

3.1. Efficacy Endpoints

(1) Primary endpoint

The anti-PRP antibody seroprotection (antibody titer $\geq 1 \mu\text{g/mL}$) rate, and the seroprotection rates for pertussis, diphtheria toxin, tetanus toxin, and attenuated polio virus at 4 weeks after the primary immunization.

(2) Secondary Endpoints

- (a) The anti-PRP antibody seroprotection (antibody titer $\geq 0.15 \mu\text{g/mL}$) rate and the geometric mean antibody titer for anti-PRP antibodies at 4 weeks after the primary immunization
- (b) The geometric mean antibody titers for pertussis, diphtheria toxin, tetanus toxin, and attenuated poliovirus at 4 weeks after the primary immunization
- (c) The anti-PRP antibody seroprotection (antibody titer $\geq 1 \mu\text{g/mL}$) rate, the anti-PRP antibody seroprotection (antibody titer $\geq 0.15 \mu\text{g/mL}$) rate and the geometric mean antibody titer for anti-PRP antibodies at 4 weeks after the booster immunization.
- (d) The antibody seroprotection rates and geometric mean antibody titers for pertussis, diphtheria toxin, tetanus toxin, and attenuated polio virus at 4 weeks after the booster immunization.

3.2. Safety Endpoints

Adverse events and adverse drug reactions

3.3. Other Endpoints

None

4. DEFINITIONS OF DERIVED VARIABLES AND TABULATION METHODS

4.1. Methods of Derivation

(1) Age in months

The age in months will be calculated based on the date of the first vaccine dose and the date of birth. The difference between the date in question (YYYY1/MM1/DD1) and the date of birth (YYYY2/MM2/DD2) will be defined as A.

$$A = (YYYY1 - YYYY2) \times 12 + (MM1 - MM2)$$

If DD1 < DD2, then the age in full months will be A - 1.

If DD1 \geq DD2, then the age in full months will be A.

(2) Age in months at adverse event onset

The age in months at adverse event onset will be calculated from the date of onset of the adverse event and the date of birth. Additionally, the date in question in “4.1. (1) Age in Months” in this document will be reclassified as the date of adverse event onset in the calculation formula.

(3) Number of days from the immediately preceding dose of investigational product to adverse event onset

The “number of days from the immediately preceding dose of investigational product to adverse event onset” will be calculated as the day of adverse event onset minus the day of the immediately preceding dose. Furthermore, the day of adverse event onset will be the “day on which symptoms were observed or the day of the test that yielded abnormal findings.”

(4) Adverse event duration

Adverse event duration = Date of outcome – Date of onset + 1 (in days)

4.2. Methods of Tabulation

(1) Antibody titer geometric mean and geometric standard deviation

Antibody titer geometric mean = $10^{(\text{mean of the log-transformed value (base 10) of the antibody titer})}$

Antibody titer geometric standard deviation = $10^{(\text{standard deviation of the log-transformed value (base 10) of the antibody titer})}$

Antibody titer geometric mean 95% confidence interval

= $10^{(\text{lower limit of the 95% confidence interval of the mean of the log-transformed value (base 10) of the antibody titer})}$ to $10^{(\text{upper limit of the 95% confidence interval of the mean of the log-transformed value (base 10) of the antibody titer})}$

However, for the anti-polio antibody titers (anti-poliovirus antibody titers [type 1, type 2, type 3]), because the data obtained are base 2 log-transformed values, they will be calculated as shown below. In this case, the data obtained will be calculated as “the log-transformed values (base 2) of the antibody titers.”

Antibody titer geometric mean = $2^{(\text{mean of the log-transformed value (base 2) of the antibody titer})}$

Antibody titer geometric standard deviation = $2^{(\text{standard deviation of the log-transformed value (base 2) of the antibody titer})}$

Antibody titer geometric mean 95% confidence interval

= $2^{(\text{lower limit of the 95% confidence interval of the mean of the log-transformed value (base 2) of the antibody titer})}$ to $2^{(\text{upper limit of the 95% confidence interval of the mean of the log-transformed value (base 2) of the antibody titer})}$

(2) Seroprotection rates

Table 4.2

Measurement Parameter		Measurement Method	Reference Value
Hib	Anti-PRP antibody concentrations	Enzyme-linked	$\geq 1 \mu\text{g/mL}$

		immunosorbent assay (ELISA)	$\geq 0.15 \mu\text{g/mL}$
Diphtheria	Anti-diphtheria antibody concentrations (Both [REDACTED])	Neutralization method	$\geq 0.1 \text{ IU/mL}$
Pertussis	Anti-pertussis antibody concentrations	Enzyme-linked immunosorbent assay (ELISA)	$\geq 10.0 \text{ EU/mL}$
	Anti-FHA antibody concentrations		$\geq 10.0 \text{ EU/mL}$
Tetanus	Anti-tetanus antibody concentrations	Indirect agglutination (KPA)	$\geq 0.01 \text{ IU/mL}$
Polio	Anti-poliovirus antibody titers* (types 1, 2, and 3)	Neutralization method	$\geq 8\text{-fold}$

The proportions of subjects with the aforementioned reference antibody titers following vaccination with the investigational product will be calculated.

Seroprotection rate (%) =

$[(\text{Number of subjects with antibodies}) / (\text{Number of subjects evaluated for efficacy})] \times 100$

The number of subjects assessed for efficacy will be the number of subjects for whom antibody titer results have been obtained.

(3) Adverse drug reactions

Adverse events for which it is thought there is a reasonable possibility of there being a causal relationship with the investigational product are considered adverse drug reactions.

5. ANALYSIS SETS

The analysis of efficacy is performed in the full analysis set (FAS). In addition, safety analysis is performed in the safety analysis set.

The analysis sets are defined below. Detailed rules about subject handling will be decided by the study sponsor before the database lock

5.1. Efficacy Analysis Sets

The FAS will consist of all randomized subjects except for the following subjects.

- Subjects who did not take the investigational product at all
- Subjects for whom no antibody titer results at all could be obtained at 4 weeks after the primary immunization

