6.2. Allowable Assessment Time Point Deviation Window

For the tabulation at each time point of test and observation parameters, data meeting the allowable time window in days specified in “9.1 Test/Observation Schedule” of the study protocol will be used, and data will not be replaced using data from outside the allowable windows.

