7.1.6. Tabulation Time Points and Baselines

The tabulation time points will be displayed as shown in the table below. The baseline will be "Before

the first dose at Visit 1.”

Table 7.1.5: Tabulation Time Points

Notation for Tabulation		Assessment Time Points in the Protocol
Assessment Time Point	Abbreviation	
Before the first vaccination	V1	Before the first dose at Visit 1
4 weeks after the primary immunization	V4	Post-vaccination examination at Visit 4
Before the booster immunization	V5	Before the fourth dose at Visit 5
4 weeks after the booster immunization	V6	Postdose examination 2 at Visit 6 and at discontinuation

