7.5. Efficacy Analyses

7.5.1. Primary endpoints

Analysis population(s): FAS

Analysis parameter: The anti-PRP antibody seroprotection (antibody titer ≥ 1 $\mu\text{g/mL}$) rate, and also the seroprotection rate for other antibodies (anti-diphtheria antibodies [REDACTED], anti-PT antibodies, anti-FHA antibodies, anti-tetanus antibodies, anti-poliovirus serotype 1 antibodies, anti-poliovirus serotype 2 antibodies, anti-poliovirus serotype 3 antibodies).

Analysis method: For each analysis parameter, the number of subjects, the number of subjects assessed for efficacy based on each antibody, the number of seroprotections, the seroprotection rate (%), and the two-sided, 95% confidence intervals will be calculated by group and time point (at 4 weeks after the primary immunization and at 4 weeks after the booster immunization).

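### Cohort 1 booster endpoints are analysed in a set that requires a post-primary titre, so an infant with no Visit 4 titre at all loses a valid booster result

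*SAP*

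**What the plan says.** All references are to the Cohort 1 SAP unless stated.

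- **Analysis set.** Section 5 assigns all efficacy analysis to the FAS. Section 5.1 excludes infants who received no investigational product and "Subjects for whom no antibody titer results at all could be obtained at 4 weeks after the primary immunization". Protocol 13.1 defines the same set, and neither document defines a separate set for the booster.
- **Booster endpoints.** Section 3.1 lists, as (c), anti-PRP rates and geometric mean titre after the booster and, as (d), the rates and geometric mean titres for the other antigens at the same time point.
- **Where the FAS is used.** Sections 7.5.1 and 7.5.2.1 name the FAS and report results "at 4 weeks after the primary immunization and at 4 weeks after the booster immunization". The titre profiles in 7.5.2.2 and the added diphtheria analyses in 7.5.3 also use it.
- **Denominator.** Section 4.2: "The number of subjects assessed for efficacy will be the number of subjects for whom antibody titer results have been obtained".
- **Windows.** Section 6.2 restricts tabulation to in-window data and adds that "data will not be replaced using data from outside the allowable windows".
- **Time-point labels.** In Table 7.1.5, V4 is "Post-vaccination examination at Visit 4" and nothing else, while V6 takes Visit 6 and also discontinuation samples.

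**The concern.** The exclusion suits the post-primary endpoints. In the Cohort 2 SAP, where follow-up ends at Visit 4, it raises no difficulty. Cohort 1 goes on to a fourth dose and a second post-vaccination sample, and the set definition was not adapted. Whether an infant can be counted after the booster then depends on a sample taken before it.

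Cohort 1 is the only cohort that receives BK1310 as the booster. Under Protocol 5.2.1, Cohort 2 infants get their booster through, for example, routine immunization, and Cohort 3 measures titres after that dose. With a target of 15 infants per group, each valid booster titre counts, and one infant is 1/15 = 6.7% of a group.

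**Working it through.** **Can the case arise under the plan?**

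1. Dose 4 is timed from Visit 3 (6 to 13 months later, SAP 2.4), so it does not depend on Visit 4 having been completed.
2. The discontinuation criteria in Protocol 12.1 do not require withdrawal of an infant whose Visit 4 sample is missing or unusable.
3. Such an infant can therefore receive dose 4 and give a post-booster sample. SAP 5.1 then excludes the infant from the FAS, and 7.5.1, 7.5.2.1, 7.5.2.2 and 7.5.3 take their booster results from the FAS only.
4. If the Visit 4 condition did not apply at the booster time point, 4.2 would still count only infants with a result there. The condition does no missing-data work that 4.2 leaves undone.

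**Effect on precision.** Inputs: 15 per group (SAP 2.5) and Clopper-Pearson two-sided 95% intervals (SAP 7.1.3). When all n infants respond, the lower limit is 0.025^(1/n).

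| Infants lost | Result | Lower limit | Drop from previous row |
|---|---|---|---|
| 0 | 15/15 | 0.025^(1/15) = 78.2% | |
| 1 | 14/14 | 0.025^(1/14) = 76.8% | 1.4 points |
| 2 | 13/13 | 0.025^(1/13) = 75.3% | 1.5 points |

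The range of 0 to 2 lost per group is an assumption.

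**Effect on the estimate, as an illustration only.** If the one infant lost were also the only non-responder, the report would show 14/14 = 100% (76.8 to 100) where the full data give 14/15 = 93.3% (68.1 to 99.8).

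**How often.** The documents give no rate of missing Visit 4 titres. If each infant independently lacks all Visit 4 titres with probability m, the chance of at least one among 30 is 1 − (1 − m)^30:

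| Assumed m | Chance of at least one in 30 | Expected number (30m) |
|---|---|---|
| 1% | 26% | 0.3 |
| 2% | 45% | 0.6 |
| 5% | 79% | 1.5 |
| 10% | 96% | 3.0 |

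These overstate the chance of losing a booster result, because the infant must also receive dose 4 and give a usable sample.

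The plan has no figure of its own to reproduce. The Cohort 1 sample size is stated without an expected rate, precision target or dropout allowance.

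**The case against.** Four points can be made for the plan.

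- **The trigger is narrow.** Only an infant with no result for any of the eight antibodies at Visit 4 is excluded; one result for one antigen keeps the infant in. The decision to start Cohort 2 rests on the post-primary anti-PRP results (Protocol 5.2.1 and 5.2.2), so sites and sponsor have reason to secure that sample. This stands.
- **The window rule does not clearly add to it.** A reader might infer that a Visit 4 sample drawn a day late also costs the infant the booster result. The documents do not support that. Section 6.2 governs tabulation by time point, not membership of the set, and a late sample still yields results. Section 5 leaves subject-handling detail to the sponsor before database lock, so the question is open.
- **A common set has some use.** Keeping one population helps the titre profiles across V1, V4, V5 and V6 describe the same infants. It would therefore be too strong to say that the exclusion serves no purpose, although the SAP states none.
- **The consequence is limited.** The endpoints are secondary, no significance level is set, and no decision rule in the plan uses V6. A reader might also infer that booster rates will be inflated. That needs the lost infant to be a non-responder, and nothing in the documents suggests it.

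None of this removes the exclusion as written. The deferred handling rules could do so, but no written rule does.

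**Conclusion.** The point holds as a minor defect in the analysis-set definition. As written, the Cohort 1 SAP discards the valid booster titres of an infant with no Visit 4 titre at all. If all infants respond, each one lost takes about 1.4 to 1.5 points off the exact lower limit in a group of 15. This rests on full enrolment of 15 per group and on an unknown number affected, which may be zero. Whether an out-of-window Visit 4 sample also triggers exclusion is not stated. The change is worth making because it costs little and protects precision in the only cohort given a BK1310 booster.

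**What to change.** 1. In SAP 5.1, add a booster set: all randomised subjects who received dose 4 and have at least one antibody titre 4 to 6 weeks after dose 4, whether sampled at Visit 6 or at discontinuation after dose 4. Use it for the booster time point in 7.5.1, 7.5.2.1, 7.5.2.2 and 7.5.3. Naming discontinuation samples matters, because Protocol 12.2 seeks blood 4 to 6 weeks after vaccination from infants who stop after dose 4, and a set restricted to Visit 6 would lose those results.
2. Keep the current FAS for the primary-series endpoints, and state whether an out-of-window Visit 4 sample counts towards membership.
3. Correct Table 7.1.5 so that a discontinuation sample taken after dose 3 is not tabulated as V6. The Cohort 2 SAP's table already places such samples at V4.
4. Record the change in SAP section 9, which currently reports no changes from the protocol, and give the reason there and in the study report, as Protocol 13.4 requires.

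**Cost:** a definition, edits to the population lines, one table row and an entry in section 9; no new data. The downside is that populations differ between time points, so the titre profiles no longer follow exactly the same infants. The tables already show the number assessed.
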